8.2. Adverse Events of Interest Analyses

There are no pre-defined Adverse Events of Special Interest in the protocol, as it was a first time in human (FTIH) trial. During the course of the study, the analyses of the following adverse events of interest were included upon the safety review team (SRT) requests.

- Corneal events
- Thrombocytopenia
- Neutropenia
- Hematologic Toxicity
- Infusion-related Reactions as collected in the eCRF

For Corneal events, Thrombocytopenia, Neutropenia Hematologic Toxicity, a comprehensive list of MedDRA terms based on clinical review will be used to identify each type of event. Changes to the MedDRA dictionary may occur between the start of the study and the time of reporting and/or emerging data from on-going studies may highlight additional adverse events of interest, therefore the list of terms to be used for each event of interest and the specific events of interest will be based on the SRT agreements in place at the time of reporting. The details of the planned displays are provided in [Appendix 12: List of Data Displays](#).

Summaries of the number and percentage of subjects with these events will be provided for each type of events separately by preferred term and maximum grade. The time of

onset and duration of first occurrence of each type of events will be summarized using summary statistics mean, standard deviation, median, minimum value, and maximum. The number and percentage of subjects who have time of onset of first occurrence (1-21, 22-42, 43-63, >63 days) will be reported. The number and percentage of subjects who have duration of first occurrence (1-21, 22-42, >42 days) will be reported.

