5. On initial (first infusion) dosing day, vital signs must be assessed at pre-dose (within 30 minutes prior to SOI), +10 minutes, +30 minutes (±15 min) after SOI, EOI, and 1 hour post EOI. On subsequent dosing days, vital signs must be assessed at pre-dose (within 30 minutes prior to SOI), +30 minutes after SOI, and EOI. **On days where vital sign timepoints align with PK sampling timepoints, vital signs should be assessed prior to PK samples being drawn.**
6. If completed within 72 hrs prior to the first dose, this assessment need not be repeated on Day 1 of Cycle 1. Refer to Table 15 of the protocol for a comprehensive list of lab tests.
7. Troponin will be measured at the local (troponin I or T) and central (troponin I) lab.
8. CK-MB at the local lab or if not available by a central laboratory.
9. BNP to be measured locally, or if not available by a central laboratory, at screening; if cardiac workup is required due to safety concerns during the study, BNP should be measured.

10. Perform only in women of child-bearing potential. A serum pregnancy test should be performed at screening, and subsequent pregnancy tests may be either serum or urine.
11. Final pregnancy test (serum or urine) must be performed in women of childbearing potential 60 days after last study treatment.
12. ECGs to be performed in triplicate. On dosing days, ECG to be performed at predose (within 30 minutes prior to SOI) and EOI. At screening, on interim visits (C1D8 and C1D15) and End of Study, obtain a single ECG measurement. **On days where ECG timepoints align with PK sampling timepoints, ECGs should be performed prior to PK samples being drawn (PK sample should be taken at the exact nominal time; refer to footnote 24)**
13. At Screening, LVEF may be performed within 30 days prior to first dose. All ECHOs indicated on dosing days may be performed up to 5 days before dosing. ECHOs to be done locally and sent to GSK for central imaging storage.
14. May be performed up to 21 days prior to C1D1 as screening value. Needs to be performed with the same method throughout the study as was done at baseline (i.e. if PET scan was used as baseline, subject needs to be followed by PET scans). Selected target lesion needs to be measured and followed over time.
15. Samples from within 14 days prior to first dose are acceptable.

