3.0401	All Treated	OECG2B	Summary of Worst-case Amount of Increase from Baseline Value in Fridericia's QTc (Part 2 MM)	Report for: Part 2 MM, (Summarize: only for 3.4 MM) Include only 'worst-case post-baseline'	SAC [A]
3.0402	All Treated	OECG2B	Summary of Worst-case Amount of Increase from Baseline Value in Fridericia's QTc (All Treated MM)	Report for: All Treated MM, (Summarize: Total). Include only 'worst-case post-baseline'	SAC [A]
3.0403	All Treated	OECG2B	Summary of Worst-case Amount of Increase from Baseline Value in Fridericia's QTc (Part 2 NHL)	Report for: Part 2 NHL, (Summarize: Total). Include only 'worst-case post-baseline'	SAC
3.0380	All Treated	EG2	Summary of Change from Baseline in ECG Values by Visit (Part 1)	Report for: Part 1, (Summarize by ascending dose level, Total). Include baseline values.	SAC [A]
3.0381	All Treated	EG2	Summary of Change from Baseline in ECG Values by Visit (Part 2 MM)	Report for: Part 2 MM, (Summarize: only for 3.4 MM). Include baseline values.	SAC [A]
3.0382	All Treated	EG2	Summary of Change from Baseline in ECG Values by Visit (All Treated MM)	Report for: All Treated MM, (Summarize for Total). Include baseline values.	SAC [A]
3.0383	All Treated	EG2	Summary of Change from Baseline in ECG Values by Visit (Part 2 NHL)	Report for: Part 2 NHL, (Summarize for Total). Include baseline values.	SAC

Safety: Tables					
No.	Population	IDSL / Example Shell	Title	Programming Notes	Deliverable [Priority]
Vital Signs					
3.0220	All Treated	VS1	Summary of Change from Baseline in Vital Signs (Part 1)	Report for: Part 1, (Summarize: by ascending dose level, Total). Add Cycle, Visit. Include baseline values.	SAC [A]
3.0221	All Treated	VS1	Summary of Change from Baseline in Vital Signs (Part 2 MM)	Report for: Part 2 MM, (Summarize: only for 3.4 MM) Add Cycle, Visit. Include baseline values.	SAC [A]
3.0222	All Treated	VS1	Summary of Change from Baseline in Vital Signs (All Treated MM)	Report for: All Treated MM, (Summarize: Total). Add Cycle, Visit. Include baseline values.	SAC [A]
3.0223	All Treated	VS1	Summary of Change from Baseline in Vital Signs (Part 2 NHL)	Report for: Part 2 NHL, (Summarize: only for 3.4 NHL) Add Cycle, Visit. Include baseline values.	SAC
3.0230	All Treated	OVT1B	Summary of Changes in Heart Rate from Baseline (Part 1)	Report for: Part 1, (Summarize: by ascending dose level, Total). Include only 'worst-case post-baseline'	SAC [A]

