3.0231	All Treated	OVT1B	Summary of Changes in Heart Rate from Baseline (Part 2 MM)	Report for: Part 2 MM, (Summarize: only for 3.4 MM) Include only 'worst-case post-baseline'	SAC [A]
3.0232	All Treated	OVT1B	Summary of Changes in Heart Rate from Baseline (All Treated MM)	Report for: All Treated MM, (Summarize: Total). Include only 'worst-case post-baseline'	SAC [A]

CONFIDENTIAL

BMA117159

Safety: Tables					
No.	Population	IDSL / Example Shell	Title	Programming Notes	Deliverable [Priority]
3.0233	All Treated	OVT1B	Summary of Changes in Heart Rate from Baseline (Part 2 NHL)	Report for: Part 2 NHL, (Summarize: only for 3.4 NHL) Include only 'worst-case post-baseline'	SAC
3.0240	All Treated	OVT2B	Summary of Increases in Systolic Blood Pressure from Baseline (Part 1)	Report for: Part 1, (Summarize: by ascending dose level, Total).	SAC [A]
3.0241	All Treated	OVT2B	Summary of Increases in Systolic Blood Pressure from Baseline (Part 2 MM)	Report for: Part 2 MM, (Summarize: only for 3.4 MM)	SAC [A]
3.0242	All Treated	OVT2B	Summary of Increases in Systolic Blood Pressure from Baseline (All Treated MM)	Report for: All Treated MM, (Summarize: Total). Include only 'worst-case post-baseline'	SAC [A]
3.0243	All Treated	OVT2B	Summary of Increases in Systolic Blood Pressure from Baseline (Part 2 NHL)	Report for: Part 2 NHL, (Summarize: only for 3.4 NHL) Include only 'worst-case post-baseline'	SAC
3.0250	All Treated	OVT2B	Summary of Increases in Diastolic Blood Pressure from Baseline (Part 1)	Report for: Part 1, (Summarize: by ascending dose level, Total). Include only 'worst-case post-baseline'	SAC [A]
3.0251	All Treated	OVT2B	Summary of Increases in Diastolic Blood Pressure from Baseline (Part 2 MM)	Report for: Part 2 MM, (Summarize: only for 3.4 MM) Include only 'worst-case post-baseline'	SAC [A]
3.0252	All Treated	OVT2B	Summary of Increases in Diastolic Blood Pressure from Baseline (All Treated MM)	Report for: All Treated MM, (Summarize: Total). Include only 'worst-case post-baseline'	SAC [A]

Safety: Tables					
No.	Population	IDSL / Example Shell	Title	Programming Notes	Deliverable [Priority]
3.0253	All Treated	OVT2B	Summary of Increases in Diastolic Blood Pressure from Baseline (Part 2 NHL)	Report for: Part 2 NHL, (Summarize: only for 3.4 NHL) Include only 'worst-case post-baseline'	SAC

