3.0260	All Treated	OVT1B	Summary of Changes in Temperature from Baseline (Part 1)	Report for: Part 1, (Summarize: by ascending dose level, Total). Include only 'worst-case post-baseline'	SAC [A]
3.0261	All Treated	OVT1B	Summary of Changes in Temperature from Baseline (Part 2 MM)	Report for: Part 2 MM, (Summarize: only for 3.4 MM) Include only 'worst-case post-baseline'	SAC [A]
3.0262	All Treated	OVT1B	Summary of Changes in Temperature from Baseline (All Treated MM)	Report for: All Treated MM, (Summarize: Total). Include only 'worst-case post-baseline'	SAC [A]
3.0263	All Treated	OVT1B	Summary of Changes in Temperature from Baseline (Part 2 NHL)	Report for: Part 2 NHL, (Summarize: only for 3.4 NHL) Include only 'worst-case post-baseline'	SAC
ECOG Performance Status					
3.0410	All Treated	PS1A	Summary of ECOG Performance Status (Part 1)	Report for: Part 1, (Summarize: by ascending dose level, Total).	SAC [A]
3.0411	All Treated	PS1A	Summary of ECOG Performance Status (Part 2 MM)	Report for: Part 2 MM, (Summarize: only for 3.4 MM)	SAC [A]
3.0412	All Treated	PS1A	Summary of ECOG Performance Status (All Treated MM)	Report for: All Treated MM, (Summarize: Total).	SAC [A]

CONFIDENTIAL

BMA117159

Safety: Tables					
No.	Population	IDSL / Example Shell	Title	Programming Notes	Deliverable [Priority]
3.0413	All Treated	PS1A	Summary of ECOG Performance Status (Part 2 NHL)	Report for: Part 2 NHL, (Summarize: only for 3.4 NHL)	SAC
3.0420	All Treated	PS3A	Summary of Change in ECOG Performance Status from Baseline (Part 1)	Report for: Part 1, (Summarize: by ascending dose level, Total).	SAC [A]
3.0421	All Treated	PS3A	Summary of Change in ECOG Performance Status from Baseline (Part 2 MM)	Report for: Part 2 MM, (Summarize: only for 3.4 MM)	SAC [A]
3.0422	All Treated	PS3A	Summary of Change in ECOG Performance Status from Baseline (All Treated MM)	Report for: All Treated MM, (Summarize: Total).	SAC [A]
3.0423	All Treated	PS3A	Summary of Change in ECOG Performance Status from Baseline (Part 2 NHL)	Report for: Part 2 NHL, (Summarize: only for 3.4 NHL)	SAC
Left Ventricular Ejection Fraction					
3.0480	All Treated	OLVEF1 A	Summary of Left Ventricular Ejection Fraction Change from Baseline (Part 1)	Report for: Part 1, (Summarize: by ascending dose level, Total).	SAC [A]
3.0481	All Treated	OLVEF1 A	Summary of Left Ventricular Ejection Fraction Change from Baseline (Part 2 MM)	Report for: Part 2 MM, (Summarize: only for 3.4 MM)	SAC [A]

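### All eight categorical blood pressure tables cover increases only, so no table gives the number and percentage of subjects with a measured fall

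*SAP*

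**What the plan says.** The vital signs tables are in SAP 16.12.8. The systolic set (3.0240-3.0243) and the diastolic set (3.0250-3.0253) use shell OVT2B and are titled as increases; the Part 2 myeloma rows read "Summary of Increases in Systolic Blood Pressure from Baseline (Part 2 MM" and "Summary of Increases in Diastolic Blood Pressure from Baseline (Part 2 MM". Heart rate (3.0230-3.0233) and temperature (3.0260-3.0263) use shell OVT1B and are titled as changes: "Summary of Changes in Heart Rate from Baseline (Part 2 MM" and "Summary of Changes in Temperature from Baseline (Part 2 MM". The only other vital signs table is a by-cycle, by-visit summary on shell VS1 (3.0220-3.0223), "Summary of Change from Baseline in Vital Signs (Part 2 MM".

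Section 8.7 says that vital signs follow the sponsor's core data standards and gives no categories for them. Section 16.8.2 leaves the limits to the sponsor's IDSL standard.

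On timing, footnote 5 of the expansion schedule for myeloma (16.2.3.1) says that on the first dosing day "vital signs must be assessed at pre-dose (within 30 minutes prior to SOI), +10 minutes, +30 minutes", followed by readings at the end of infusion and one hour later. On later dosing days, "vital signs must be assessed at pre-dose (within 30 minutes prior to SOI), +30 minutes after SOI, and EOI". Section 8.2 names "Infusion-related Reactions as collected in the eCRF" as one of five adverse events of interest. Section 2.2 includes changes in clinical signs in the primary endpoint.

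**The concern.** The schedule collects blood pressure when a fall during infusion could be seen, and the primary endpoint does not restrict changes in clinical signs to one direction. The tables that would turn those readings into subject counts then cover only rises. A reader of the study report could see how many subjects at each dose level had a rise, but not how many had a fall. For an intravenous drug with infusion reactions as an event of interest, the missing direction is informative. The plan gives no reason for treating blood pressure differently from heart rate and temperature.

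**Working it through.** No formula applies; the check is a reading of the display list against the rules that feed it.

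**1. Count the categorical vital signs tables (16.12.8).**

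| Parameter | Tables | Shell | Title covers |
|---|---|---|---|
| Systolic pressure | 3.0240-3.0243 (4) | OVT2B | increases |
| Diastolic pressure | 3.0250-3.0253 (4) | OVT2B | increases |
| Heart rate | 3.0230-3.0233 (4) | OVT1B | changes |
| Temperature | 3.0260-3.0263 (4) | OVT1B | changes |

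Blood pressure: 4 + 4 = 8 tables, all 8 for increases and 0 for decreases. Heart rate and temperature: 4 + 4 = 8 tables, all 8 for changes.

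**2. What is collected (16.2.3.1, footnote 5).** At the first infusion there are five time points: pre-dose, +10 minutes, +30 minutes, end of infusion and one hour after. Four of them follow the start of infusion. At later infusions there are three: pre-dose, +30 minutes and end of infusion. Two of them follow the start.

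**3. Follow a measured fall through the displays.**
- *At a planned time, not reported as an adverse event.* It enters the VS1 summary for that visit, which aggregates over subjects. It may appear in listing 30.0440 (myeloma) or 30.0441 (lymphoma) if it meets the IDSL limits. Neither display counts subjects with a fall.
- *At an unscheduled visit.* Section 16.5.2 keeps unscheduled visits out of by-planned-time summaries and admits them to worst-case analyses and listings. No worst-case table covers falls, so such a measurement reaches no table and can appear only in a listing.
- *Reported by the investigator.* It is counted by subject in the adverse event tables (for example 3.0030 and 3.0910, by dose level) and, if recorded as an infusion reaction, in 3.0110-3.0113, 3.0600-3.0603 and 3.0880-3.0883.

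**4. Compare with the SAP's own practice.** Section 8.6 summarises laboratory tests graded in both directions separately by direction. For ungraded tests it counts a subject with both a low and a high shift under each. Section 16.6.1 applies the same double counting to high and low values of safety parameters.

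**5. Check the programming notes.** Six of the eight blood pressure rows restrict the table to the worst case post-baseline. Rows 3.0240 (systolic, Part 1) and 3.0241 (systolic, Part 2 myeloma) lack that note. As written, it is unclear for these two whether unscheduled visits count.

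**The case against.** The strongest reply has four parts.

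- **The shells are not in the document.** OVT2B, OVT1B and VS1 are library displays, so their content is inferred from titles. This stands as a limit. But the titles differ consistently by parameter and shell, and nothing in 8.7 or 16.8.2 says that OVT2B also shows decreases.
- **Falls that matter clinically are counted already.** Those reported as adverse events or infusion reactions have subject counts, and infusion reactions also have a figure of proportions (13.0160-13.0161). This stands, but it depends on the investigator reporting the event; measured vital signs serve as an independent record.
- **Other displays show extremes.** The continuous summaries that the SAP spells out (6.3, 6.5, 8.6) include a minimum and a maximum, so VS1 probably shows the largest fall at each planned visit. The listings may show low values and could be read by hand in an expansion cohort of at most 40 subjects (3.1.2.1.1). Neither is a number and percentage by dose level.
- **One-directional tables are used elsewhere and no two-directional count was promised.** The QTc tables count increases only. For QTc, however, 8.7 sets out upward grades and ranges of change explicitly; for blood pressure it says nothing about direction.

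A reader might infer that falls are never tabulated by subject, or that the report would present the drug as free of them. The documents support neither. Reported events are tabulated, and a table titled as increases makes no statement about decreases.

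**Conclusion.** The point holds for measured values in categorical tables: 8 of 8 blood pressure tables are for increases, 0 of 8 for decreases, and no other listed table supplies the number and percentage of subjects with a measured fall. The gap is widest for falls seen only at unscheduled visits, which no table picks up unless they are reported as events.

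This rests on the table titles and their contrast with heart rate and temperature, because the shells and IDSL limits are not shown. The SAP gives no spread for blood pressure change, so the number of falls that would go uncounted cannot be estimated from it. The plan does not contradict itself here and no decision rule depends on these tables. This is a cheap improvement to the reporting of part of the primary endpoint, not an error that undermines a conclusion.

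**What to change.** In 16.12.8, retitle Tables 3.0240-3.0243 and 3.0250-3.0253 as changes and add worst-case post-baseline decrease categories beside the increase categories, taking the limits from the sponsor's display standard. Count a subject with both extremes in both directions, as 8.6 and 16.6.1 do. Add the missing worst-case post-baseline note to 3.0240 and 3.0241, so that all eight tables use unscheduled visits in the same way.

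While making the edit, state whether readings taken after the start of the first infusion count as post-baseline. Section 16.4.1 classes the first dosing day as pre-treatment for vital signs, which could keep the first-infusion readings out of either direction.

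The cost is programming on data already collected, slightly longer tables and a departure from the library shell. If OVT2B already reports decreases, a corrected title and one sentence in 8.7 are enough for the direction.

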16.12.9. Safety Figures

Safety: Figures					
No.	Population	IDSL / Example Shell	Title	Programming Notes	Deliverable [Priority]
Laboratory					
13.0130	All Treated	LIVER14	Scatter Plot of Maximum vs. Baseline for ALT (Part 1)	Report for sub-population: Part 1. Pool all subjects together.	SAC [A]
13.0131	All Treated	LIVER14	Scatter Plot of Maximum vs. Baseline for ALT (Part 2 MM)	Report for sub-population: Part 2 MM.	SAC [A]
13.0133	All Treated	LIVER14	Scatter Plot of Maximum vs. Baseline for ALT (Part 2 NHL)	Report for sub-population: Part 2 NHL.	SAC
13.0120	All Treated	LIVER9	Scatter Plot of Maximum Bilirubin versus Maximum ALT - eDISH (Part 1)	Report for sub-population: Part 1. Pool all subjects together.	SAC [A]
13.0121	All Treated	LIVER9	Scatter Plot of Maximum Bilirubin versus Maximum ALT - eDISH (Part 2 MM)	Report for sub-population: Part 2 MM.	SAC [A]
13.0122	All Treated	LIVER9	Scatter Plot of Maximum Bilirubin versus Maximum ALT - eDISH (Part 2 NHL)	Report for sub-population: Part 2 NHL.	SAC [A]
13.0140	All Treated	LIVER9	Scatter Plot of Maximum AST vs Maximum LDH - eDISH Plot (Part 1)	Report for sub-population: Part 1. Pool all subjects together. Bold reference lines are not needed. Do not include Hy's Quadrant and Temple's Corollary.	SAC [A]
13.0141	All Treated	LIVER9	Scatter Plot of Maximum AST vs Maximum LDH - eDISH Plot (Part 2 MM)	Report for sub-population: Part 2 MM. Do not include Hy's Quadrant and Temple's Corollary.	SAC [A]

CONFIDENTIAL

BMA117159

Safety: Figures					
No.	Population	IDSL / Example Shell	Title	Programming Notes	Deliverable [Priority]
13.0142	All Treated	LIVER9	Scatter Plot of Maximum AST vs Maximum LDH - eDISH Plot (Part 2 NHL)	Report for sub-population: Part 2 NHL. Do not include Hy's Quadrant and Temple's Corollary.	SAC
13.0150	All Treated	LIVER9	Scatter Plot of Maximum AST vs Maximum Creatinine Kinase - eDISH Plot (Part 1)	Report for sub-population: Part 1. Pool all subjects together. Bold reference lines are not needed. Do not include Hy's Quadrant and Temple's Corollary.	SAC [A]
13.0151	All Treated	LIVER9	Scatter Plot of Maximum AST vs Maximum Creatinine Kinase - eDISH Plot (Part 2 MM)	Report for sub-population: Part 2 MM. Do not include Hy's Quadrant and Temple's Corollary.	SAC [A]
13.0152	All Treated	LIVER9	Scatter Plot of Maximum AST vs Maximum Creatinine Kinase - eDISH Plot (Part 2 NHL)	Report for sub-population: Part 2 NHL. Do not include Hy's Quadrant and Temple's Corollary.	SAC
Adverse Events					
13.0160	All Treated	SAFE_F1	Proportions of Subjects with Infusion-related Reactions (Part 1)	Report for sub-population: Part 1. Pool all subjects together.	SAC [A]
13.0161	All Treated	SAFE_F1	Proportions of Subjects with Infusion-related Reactions (Part 2 MM)	Report for sub-population: Part 2 MM.	SAC [A]
ECG					
13.0200	All Treated	OECG4	Fridericia's QTc Shifts from Baseline to Worst-case Post Baseline (Part 1)	Report for sub-population: Part 1. Pool all subjects together. If machine read QTcF is missing, use the manual read QTcF and add footnote that Machine and Manual calculate values are	SAC [A]

Safety: Figures					
No.	Population	IDSL / Example Shell	Title	Programming Notes	Deliverable [Priority]
				collapsed together.	
13.0201	All Treated	OECG4	Fridericia's QTc Shifts from Baseline to Worst-case Post Baseline (Part 2 MM)	Report for sub-population: Part 2 MM. If machine read QTcF is missing, use the manual read QTcF, and add footnote that Machine and Manual calculate values are collapsed together	SAC [A]
13.0202	All Treated	OECG4	Fridericia's QTc Shifts from Baseline to Worst-case Post Baseline (Part 2 NHL)	Report for sub-population: Part 2 NHL. If machine read QTcF is missing, use the manual read QTcF, and add footnote that Machine and Manual calculate values are collapsed together	SAC
Patient Profile Plot					
13.0190	All Treated	SAFE_F2	Profile Plot for Patients with No Corneal Event or Grade 1 Corneal Event (Part 2 MM)	Report for sub-population: Part 2 MM.	SAC [A]
13.0191	All Treated	SAFE_F2	Profile Plot for Patients with Grade 2 or Higher Corneal Events (Part 2 MM)	Report for sub-population: Part 2 MM.	SAC [A]

NOTES:

A. Indicates which displays will be generated for the reporting effort for multiple myeloma

16.12.10. Pharmacokinetic Tables

Pharmacokinetic: Tables					
No.	Population	IDSL / Example Shell	Title	Programming Notes	Deliverable [Priority]
Concentration					
4.0010	PK	PK01	Summary of Plasma GSK2857916 (ADC) PK Concentration-Time Data (Part 1)	By dose level	SAC [A]
4.0011	PK	PK01	Summary of Plasma GSK2857916 (ADC) PK Concentration-Time Data (Part 2 MM)		SAC [A]
4.0013	PK	PK01	Summary of Plasma GSK2857916 (ADC) PK Concentration-Time Data (Part 2 NHL)		SAC
4.0020	PK	PK01	Summary of Plasma GSK2857916 (Total Antibody) PK Concentration-Time Data (Part 1)	By dose level	SAC [A]
4.0021	PK	PK01	Summary of Plasma GSK2857916 (Total Antibody) PK Concentration-Time Data (Part 2 MM)		SAC [A]
4.0023	PK	PK01	Summary of Plasma GSK2857916 (Total Antibody) PK Concentration-Time Data (Part 2 NHL)		SAC
4.0030	PK	PK01	Summary of Plasma GSK2857916 (Unbound Antibody) PK Concentration-Time Data (Part 1)	By dose level	SAC [A]
4.0031	PK	PK01	Summary of Plasma GSK2857916 (Unbound Antibody) PK Concentration-Time Data (Part 2 MM)	If data was not collected, present "No data to report"	SAC [A]
4.0033	PK	PK01	Summary of Plasma GSK2857916 (Unbound Antibody) PK Concentration-Time Data (Part 2 NHL)	If data was not collected, present "No data to report"	SAC
4.0040	PK	PK01	Summary of Plasma cys-mcMMAF PK Concentration-Time Data (Part 1)	By dose level	SAC [A]

Pharmacokinetic: Tables					
No.	Population	IDSL / Example Shell	Title	Programming Notes	Deliverable [Priority]
4.0041	PK	PK01	Summary of Plasma cys-mcMMAF PK Concentration-Time Data (Part 2 MM)		SAC [A]
4.0043	PK	PK01	Summary of Plasma cys-mcMMAF PK Concentration-Time Data (Part 2 NHL)		SAC
PK Parameter					
4.0050	PK	PK06	Summary of Derived GSK2857916 (ADC) PK Parameters (Part 1)	By dose level PK06 with both transformed and untransformed values. Also include Cmax and Ctau derived for ratio analyses.	SAC [A]
4.0051	PK	PK06	Summary of Derived GSK2857916 (ADC) PK Parameters (Part 2 MM)	PK06 with both transformed and untransformed values. Cmax and Ctau	SAC [A]
4.0053	PK	PK06	Summary of Derived GSK2857916 (ADC) PK Parameters (Part 2 NHL)	PK06 with both transformed and untransformed values. Cmax and Ctau	SAC
4.0060	PK	PK06	Summary of Derived GSK2857916 (Total Antibody) PK Parameters (Part 1)	By dose level PK06 with both transformed and untransformed values. Also include Cmax and Ctau derived for ratio analyses.	SAC [A]
4.0061	PK	PK06	Summary of Derived GSK2857916 (Total Antibody) PK Parameters (Part 2 MM)	PK06 with both transformed and untransformed values. Cmax and Ctau	SAC [A]

CONFIDENTIAL

BMA117159

Pharmacokinetic: Tables					
No.	Population	IDSL / Example Shell	Title	Programming Notes	Deliverable [Priority]
4.0063	PK	PK06	Summary of Derived GSK2857916 (Total Antibody) PK Parameters (Part 2 NHL)	PK06 with both transformed and untransformed values. Cmax and Ctau	SAC
4.0070	PK	PK06	Summary of Derived GSK2857916 (Unbound Antibody) PK Parameters (Part 1)	By dose level PK06 with both transformed and untransformed values. Also include Cmax and Ctau derived for ratio analyses.	SAC [A]
4.0071	PK	PK06	Summary of Derived GSK2857916 (Unbound Antibody) PK Parameters (Part 2 MM)	PK06 with both transformed and untransformed values. Cmax and Ctau. If data was not collected, present "No data to report"	SAC [A]
4.0073	PK	PK06	Summary of Derived GSK2857916 (Unbound Antibody) PK Parameters (Part 2 NHL)	PK06 with both transformed and untransformed values. Cmax and Ctau. If data was not collected, present "No data to report"	SAC
4.0080	PK	PK06	Summary of Derived cys-mcMMAF PK Parameter (Part 1)	By dose level PK06 with both transformed and untransformed values. Also include Cmax and Ctau derived for ratio analyses.	SAC [A]
4.0081	PK	PK06	Summary of Derived cys-mcMMAF PK Parameter (Part 2 MM)	PK06 with both transformed and untransformed values. Cmax and Ctau	SAC [A]

CONFIDENTIAL

BMA117159

Pharmacokinetic: Tables					
No.	Population	IDSL / Example Shell	Title	Programming Notes	Deliverable [Priority]
4.0083	PK	PK06	Summary of Derived cys-mcMMAF PK Parameter (Part 2 NHL)	PK06 with both transformed and untransformed values. Cmax and Ctau	SAC
4.0090	PK	PK13	Listing of Derived GSK2857916 (ADC) PK Parameters (Untransformed) (MM)		SAC [A]
4.0091	PK	PK13	Listing of Derived GSK2857916 (ADC) PK Parameters (Untransformed) (NHL)		SAC
4.0100	PK	PK13	Listing of Derived GSK2857916 (Total Antibody) PK Parameters (Untransformed) (MM)		SAC [A]
4.0101	PK	PK13	Listing of Derived GSK2857916 (Total Antibody) PK Parameters (Untransformed) (NHL)		SAC
4.0110	PK	PK13	Listing of Derived GSK2857916 (Unbound Antibody) PK Parameters (Untransformed) (MM)		SAC [A]
4.0111	PK	PK13	Listing of Derived GSK2857916 (Unbound Antibody) PK Parameters (Untransformed) (NHL)		SAC
4.0120	PK	PK13	Listing of Derived cys-mcMMAF PK Parameters (Untransformed) (MM)		SAC [A]
4.0121	PK	PK13	Listing of Derived cys-mcMMAF PK Parameters (Untransformed) (NHL)		SAC
4.0130	PK	PK03	Summary of cys-mcMMAF Pharmacokinetic Urine Excretion Data (Part 1)		SAC [A]
4.0140	PK	PK11	Listing of cys-mcMMAF Urine Excretion Data (Part 1)	replace Amount Excreted and Excretion Rate with Ae(0-24) and Fe	SAC [A]

Pharmacokinetic: Tables					
No.	Population	IDSL / Example Shell	Title	Programming Notes	Deliverable [Priority]
Dose Proportionality Analysis					
4.0150	PK	PK_T1	Summary of Results of Dose Proportionality Analysis for GSK2857916 (ADC), GSK2857916 (Total Antibody), GSL2857916 (Unbound Antibody), and cys-mcMMAF PK Parameters Using Power Model (Part 1)	Example: PPD PPD AUC(0-inf), AUC(0-t), AUC(0-τ), Cmax, and Ctrough	SAC [A]
Accumulation Ratio					
4.0160	PK	PK_T2	Summary of Results of Accumulation Ratio Assessment for GSK2857916 (ADC) PK Parameter Cmax on Day 1 of Cycle 2, 3, 5 verses Cmax on Day 1 of Cycle 1 (Part 1)	By dose level	SAC [A]
4.0161	PK	PK_T2	Summary of Results of Accumulation Ratio Assessment for GSK2857916 (ADC) PK Parameter Cmax on Day 1 of Cycle 2, 3, 5 verses Cmax on Day 1 of Cycle 1 (Part 2 MM)		SAC [A]
4.0163	PK	PK_T2	Summary of Results of Accumulation Ratio Assessment for GSK2857916 (ADC) PK Parameter Cmax on Day 1 of Cycle 2, 3, 5 verses Cmax on Day 1 of Cycle 1 (Part 2 NHL)		SAC
4.0170	PK	PK_T2	Summary of Results of Accumulation Ratio Assessment for GSK2857916 (Total Antibody) PK Parameter Cmax on Day 1 of Cycle 2, 3, 5 verses Cmax on Day 1 of Cycle 1 (Part 1)	By dose	SAC [A]
4.0171	PK	PK_T2	Summary of Results of Accumulation Ratio Assessment for GSK2857916 (Total Antibody) PK Parameter Cmax on Day 1 of Cycle 2, 3, 5 verses Cmax on Day 1 of Cycle 1 (Part 2 MM)		SAC [A]
4.0173	PK	PK_T2	Summary of Results of Accumulation Ratio Assessment for GSK2857916 (Total Antibody) PK Parameter Cmax on Day 1 of Cycle 2, 3, 5 verses Cmax on Day 1 of Cycle 1 (Part 2 NHL)		SAC

CONFIDENTIAL

BMA117159

Pharmacokinetic: Tables					
No.	Population	IDSL / Example Shell	Title	Programming Notes	Deliverable [Priority]
4.0180	PK	PK_T2	Summary of Results of Accumulation Ratio Assessment for GSK2857916 (Unbound Antibody) PK Parameter Cmax on Day 1 of Cycle 2, 3, 5 verses Cmax on Day 1 of Cycle 1 (Part 1)	By dose	SAC [A]
4.0181	PK	PK_T2	Summary of Results of Accumulation Ratio Assessment for GSK2857916 (Unbound Antibody) PK Parameter Cmax on Day 1 of Cycle 2, 3, 5 verses Cmax on Day 1 of Cycle 1 (Part 2 MM)	If data was not collected, present "No data to report"	SAC [A]
4.0183	PK	PK_T2	Summary of Results of Accumulation Ratio Assessment for GSK2857916 (Unbound Antibody) PK Parameter Cmax on Day 1 of Cycle 2, 3, 5 verses Cmax on Day 1 of Cycle 1 (Part 2 NHL)	If data was not collected, present "No data to report"	SAC
4.0190	PK	PK_T2	Summary of Results of Accumulation Ratio Assessment for cys-mcMMAF PK Parameter Cmax on Day 1 of Cycle 2, 3, 5 verses Cmax on Day 1 of Cycle 1 (Part 1)	By dose level	SAC [A]
4.0191	PK	PK_T2	Summary of Results of Accumulation Ratio Assessment for cys-mcMMAF PK Parameter Cmax on Day 1 of Cycle 2, 3, 5 verses Cmax on Day 1 of Cycle 1 (Part 2 MM)		SAC [A]
4.0193	PK	PK_T2	Summary of Results of Accumulation Ratio Assessment for cys-mcMMAF PK Parameter Cmax on Day 1 of Cycle 2, 3, 5 verses Cmax on Day 1 of Cycle 1 (Part 2 NHL)		SAC
4.0200	PK	PK_T2	Summary of Results of Accumulation Ratio Assessment for GSK2857916 (ADC) PK Parameter Ctrough on Day 1 of Cycle 2, 3, 5 verses Ctrough on Day 1 of Cycle 1 (Part 1)	By dose level	SAC [A]

CONFIDENTIAL

BMA117159

Pharmacokinetic: Tables					
No.	Population	IDSL / Example Shell	Title	Programming Notes	Deliverable [Priority]
4.0201	PK	PK_T2	Summary of Results of Accumulation Ratio Assessment for GSK2857916 (ADC) PK Parameter Ctrough on Day 1 of Cycle 2, 3, 5 verses Ctrough on Day 1 of Cycle 1 (Part 2 MM)		SAC [A]
4.0203	PK	PK_T2	Summary of Results of Accumulation Ratio Assessment for GSK2857916 (ADC) PK Parameter Ctrough on Day 1 of Cycle 2, 3, 5 verses Ctrough on Day 1 of Cycle 1 (Part 2 NHL)		SAC
4.0210	PK	PK_T2	Summary of Results of Accumulation Ratio Assessment for GSK2857916 (Total Antibody) PK Parameter Ctrough on Day 1 of Cycle 2, 3, 5 verses Ctrough on Day 1 of Cycle 1 (Part 1)	By dose	SAC [A]
4.0211	PK	PK_T2	Summary of Results of Accumulation Ratio Assessment for GSK2857916 (Total Antibody) PK Parameter Ctrough on Day 1 of Cycle 2, 3, 5 verses Ctrough on Day 1 of Cycle 1 (Part 2 MM)		SAC [A]
4.0213	PK	PK_T2	Summary of Results of Accumulation Ratio Assessment for GSK2857916 (Total Antibody) PK Parameter Ctrough on Day 1 of Cycle 2, 3, 5 verses Ctrough on Day 1 of Cycle 1 (Part 2 NHL)		SAC
4.0220	PK	PK_T2	Summary of Results of Accumulation Ratio Assessment for GSK2857916 (Unbound Antibody) PK Parameter Ctrough on Day 1 of Cycle 2, 3, 5 verses Ctrough on Day 1 of Cycle 1 (Part 1)	By dose	SAC [A]
4.0221	PK	PK_T2	Summary of Results of Accumulation Ratio Assessment for GSK2857916 (Unbound Antibody) PK Parameter Ctrough on Day 1 of Cycle 2, 3, 5 verses Ctrough on Day 1 of Cycle 1 (Part 2 MM)	If data was not collected, present "No data to report"	SAC [A]

Pharmacokinetic: Tables					
No.	Population	IDSL / Example Shell	Title	Programming Notes	Deliverable [Priority]
4.0223	PK	PK_T2	Summary of Results of Accumulation Ratio Assessment for GSK2857916 (Unbound Antibody) PK Parameter Ctrough on Day 1 of Cycle 2, 3, 5 verses Ctrough on Day 1 of Cycle 1 (Part 2 NHL)	If data was not collected, present "No data to report"	SAC
4.0230	PK	PK_T2	Summary of Results of Accumulation Ratio Assessment for cys-mcMMAF PK Parameter Ctrough on Day 1 of Cycle 2, 3, 5 verses Ctrough on Day 1 of Cycle 1 (Part 1)	By dose	SAC [A]
4.0231	PK	PK_T2	Summary of Results of Accumulation Ratio Assessment for cys-mcMMAF PK Parameter Ctrough on Day 1 of Cycle 2, 3, 5 verses Ctrough on Day 1 of Cycle 1 (Part 2 MM)		SAC [A]
4.0233	PK	PK_T2	Summary of Results of Accumulation Ratio Assessment for cys-mcMMAF PK Parameter Ctrough on Day 1 of Cycle 2, 3, 5 verses Ctrough on Day 1 of Cycle 1 (Part 2 NHL)		SAC

NOTES:

A. Indicates which displays will be generated for the reporting effort for multiple myeloma

